**Annexure 1;4**  
**Oral Health related Quality of life Questionnaire**  
**(Ten days after surgery)**

How much trouble you have with your teeth or mouth?

S.no	Questions	Score (Tick any one)				
		No trouble	A little trouble	Some trouble	Quite a lot trouble	Lots of trouble
1.	Eating/chewing foods you want					
2.	Opening your mouth wide					
3.	Sleeping					
4.	Talking to people so that they can understand you					
5.	Going about your everyday routine					
6.	Taking part in your social life					
7.	Taking part in sports					
8.	Swelling of your cheeks					
9.	Bruising					
10.	Bleeding					
11.	Nausea					
12.	Bad taste / bad breath					
13.	Food collecting in the hole after the teeth were pulled					
14.	Rate the worst pain you have felt in your teeth, mouth and face during past 24 hrs.	1	2	3	4	5
15.	Are you still taking any pain killers? (yes/no)					
16.	If yes, How many days you took and frequency					

**2. CLINICAL OUTCOMES (Annexure 2)**  
 (To be measured after 1 month post debond):

Group: open/closed	
1. Pocket Depth	
2. KT width	
3. 
 
a. Gingival recession, if any, measured on the buccal midpoint of the canine crown.
 
b. Gingival recession, if any, measured on the buccal midpoint of the L.I. crown.
 
	
4. Clinical crown length-incisal edge to gingival margin on midfacial surface parallel to the long axis.	
5. Clinical crown length-incisal edge to gingival margin on midfacial surface parallel to the long axis of the contralateral tooth	
6. Time period it took to align	DOE DOA
7. How many times did bracket debond	
8. How many times flap was raised.	
9. Probing bone level-subtracting the distance CEJ to gingival margin from the distance gingival margin to bone.	
10. Bleeding on probing	
11. Loe and silness score	

### **Operator's measure of surgical ease (Annexure 3)**

Group (open/closed):

S.NO.	QUESTION	
1.	Actual surgical time- from incision to last suture	
2.	Difficulties felt by Operator	
3.	Number of times flap was raised	
4.	No of times button debonded	
5.	Duration of traction phase till alignment of canine	

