#### Open Surgical Exposure of Impacted canine:

- Surgically uncover the canine tooth and bone removal exposing the largest diameter of the ectopic canine crown. The edges need to be substantially trimmed back and dental follicle removed to prevent regrowth of the very thick palatal mucosa. For a deeply buried and palatally displaced tooth, the exposure will additionally need to be maintained using surgical pack.
- Coe-pack surgical dressing (GC America Inc, Alsip, IL) will be left in place.
- The patient will be reviewed 10 days later, the surgical pack will be removed and the bracket will be bonded and loading will be done by traction forces. Once the tooth has

erupted sufficiently for an orthodontic attachment to be positioned at its correct location to bring the tooth into line.

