**Closed Surgical Exposure of Impacted canine:**

- Surgically, the palatal mucosal full thickness flap overlying the impacted canine will be raised and surgical bone removal exposing the largest diameter of the ectopic canine crown.
- An orthodontic attachment (button) with ligature wire and bracket with closed coil spring will be bonded to the palatal or buccal surface of the ectopic canine crown (whichever was the most accessible).

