**Secondary Outcome Measures:**

3. Pain score on the visual analogue scale [Time Frame: 10 days post-surgery], many patient reported outcomes like the number of times the bond failure take place, surgical time, pain associated with surgery will be assessed. (Annexure 3)

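### The flap-count items cannot record a repeat exposure in the open arm, and bond failure is counted by a different attachment on each of two forms

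*Protocol*

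**What the plan says.** **Repeat surgery.** Annexure 3, headed as the operator's measure of surgical ease and marked "Group (open/closed", has as item 3 "Number of times flap was raised". Annexure 2, also marked for either group, has as item 8 "How many times flap was raised". Neither form says whether the first operation counts. Neither has an item for a second exposure done without a flap.

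**Bond failure.** Secondary Outcome Measures lists "the number of times the bond failure take place" and points to Annexure 3. Item 4 there reads "No of times button debonded". Annexure 2 item 7 reads "How many times did bracket debond".

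**Technique and attachment.** The closed-technique section raises a full-thickness flap and states: "An orthodontic attachment (button) with ligature wire and bracket with closed coil spring will be bonded". The open-technique section mentions no flap. Tissue is trimmed back and the "dental follicle removed to prevent regrowth of the very thick palatal mucosa", a pack is placed, and a bracket is bonded when the pack comes off at 10 days. Step 2 of the Treatment Protocol, which names no arm, describes the bonded attachment as a button.

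**The concern.** A count can be compared between arms only if the event can occur, and can be recorded, in both. The flap items are tied to one arm's surgical technique. The open arm's counterpart, a repeat uncovering after the mucosa grows back, is an event the protocol itself treats as possible, since the trimming is meant to prevent it. The forms have nowhere to record it.

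For bond failure, two forms count two different objects for one named outcome, and no rule says which count is the outcome. Which failures enter the data then depends on the form used and on which treatment section was followed. Both problems lie in data collection. An event without a field cannot be recovered from the trial forms at analysis, at best from the clinical notes.

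**Working it through.** The protocol states no figure on this point, so there is none to reproduce. The check sets the sections side by side.

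**1. Flap items.** Section 1 (Background Knowledge) and the closed-technique section both describe a full-thickness flap for the closed arm. The same Background section describes a window in the mucosa for the open arm, and the open-technique section describes trimmed edges and a pack. Annexure 3 item 1 is consistent with a form written around the closed technique: it times surgery to the last suture, and suturing is described only for that technique.

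Let *r* and *o* be the proportions of closed-arm and open-arm patients with one repeat exposure. The protocol gives neither, so take 0 to 20% as an assumption. The difference of interest, closed minus open, is *r* − *o*.

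- First flap counted: closed mean = 1 + *r*, open mean = 0. Recorded difference = 1 + *r*, that is 1.00 to 1.20.
- First flap not counted: closed mean = *r*, open mean = 0. Recorded difference = *r*, that is 0 to 0.20.

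With *r* = *o* = 10%, the true difference is 0.10 − 0.10 = 0. The recorded difference is 1.10 on the first rule and 0.10 on the second. *o* appears in neither expression. With the planned 20 patients per arm, the expected number of open-arm re-exposures left unrecorded is 20 × *o*, from 20 × 0 = 0 to 20 × 0.20 = 4.

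**2. Bond-failure items.** The attachment named in each place:

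- Treatment Protocol step 2, no arm named: button.
- Open-technique section: bracket.
- Closed-technique section: button and bracket.
- Annexure 3 item 4, the form cited for the outcome: button.
- Annexure 2 item 7: bracket.

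Two readings follow.

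- *Step 2 governs both arms.* A button is bonded in each arm, and Annexure 3 can record failures in each. Annexure 2 would miss a button failure.
- *The technique sections govern.* The open arm has a bracket, so Annexure 3 has no place for its failures. Annexure 2 can record bracket failures in both arms but would miss a button failure in the closed arm.

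Neither item covers every attachment under both readings.

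**3. Time at risk.** The technique sections bond at surgery in the closed arm and at the 10-day review in the open arm. Background Knowledge instead puts open-arm bonding after natural eruption. The period in which a bond can fail therefore starts at different times, and neither form nor the baseline sheet records the date of first bonding.

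**The case against.** The strongest case on the other side has four parts.

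- *Flap count is not a listed outcome.* This stands. It appears only on the annexure forms, and no section says it will be compared between arms or read as a failure rate. It limits the importance of the point but does not supply the missing field.
- *Zero flaps in the open arm is inferred from silence.* This is fair, but both descriptions of the open technique give another means of access, and the inference is the natural one.
- *Counting rules can be left to an analysis plan or a form-completion guide.* This is true of whether the first flap counts. It does not help with an open-arm re-exposure, because under either rule the item as worded asks only about flaps.
- *The bracket item obviously means the study canine.* Probably so. The item names no tooth, however, and the patient wears a fixed appliance on the arch, so naming the tooth removes the doubt.

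Two stronger readings are tempting. A reader might infer that bond-failure counts differ between the arms by definition, with the button count fixed at zero in the open arm. The protocol does not support this: step 2 of the Treatment Protocol names a button without limiting it to one arm. A reader might also infer that a test on the flap count would always show a significant difference. That merely restates the assumption that every closed patient scores at least 1 and every open patient 0. It requires the first flap to be counted, and no such test is described.

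**Conclusion.** The point holds, and it is minor.

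As worded, the flap items cannot compare repeat surgery between arms, and an open-arm re-exposure has no field. This rests on the open technique using no flap, as its description implies, and does not depend on whether the first flap counts. *Repeat exposure* is this review's term; the protocol counts only flaps.

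For bond failure, the protocol uses two different counts for one secondary outcome, and its treatment sections conflict on the attachment. The size of any resulting error cannot be derived from the document. If the open-technique section governs, open-arm failures have no place on the form cited for the outcome; if step 2 governs, they do.

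The effect is limited to one secondary outcome and one unlisted form item. No primary outcome is affected.

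**What to change.** - Replace Annexure 2 item 8 and Annexure 3 item 3 with one item for both arms: *number of repeat surgical exposures of the study canine after the first operation*.
- Replace Annexure 2 item 7 and Annexure 3 item 4 with one item for both arms: *number of debonds of any attachment on the study canine, from first bonding to alignment*. Use this item as the definition of the bond-failure outcome.
- Add the date of first bonding of the study canine, so that differing times at risk can be seen and allowed for.
- Reconcile step 2 of the Treatment Protocol with the open-technique and closed-technique sections on which attachment is bonded in each arm. The first two changes make the counts usable whichever way this is settled, but they do not settle it.

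The cost is four form lines reduced to two, one added date and a short clarification of the treatment text. No extra visit or measurement is needed. The forms should be changed before they are used; for patients already treated, the missing events would have to be sought in the clinical notes.

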## **Maxillary Canine Aesthetic Index scoring sheet**

**( Annexure 4)**

Patient name: .....  
 Date of recording: .....  
 Working side: .....

Parameters investigating the previously impacted canine			
	Absent	Incomplete	Complete
Mesial papilla			
Distal papilla			
Marginal gingiva			
Recession			
Marginal gingival thickness			
Mesiodistal canine angulation			

Parameters investigating comparison between both canines			
	Major discrepancy	Minor discrepancy	No discrepancy
Curvature of marginal gingiva			
Soft tissue color and texture			
Root convexity			
Tooth morphology			
Vertical tooth position			

Parameters investigating relation previously impacted canine and neighboring teeth			
Bucco-lingual angulation crown acc. neighboring teeth			

Total score 0-3 points = excellent

4-8 points = good

9-13 points = moderate

14 or more points = poor aesthetics

Total score =

## Baseline Data

Patient's name:

Age/sex:

UID no:

Case no:

Contact number:

Address:

Side of Impaction

Severity of Impaction (Ericson and Kurol)

Angle:

Vertical height:

Sector:

Oral Hygiene:

Date of start of fixed treatment:

Date of surgical exposure:

Date of alignment of canine:

Date of debonding:

